9.2.5. Cardiovascular and Death Events

For any cardiovascular events detailed in Appendix 4 (Section 12.4) and all deaths, whether or not they are considered SAEs, specific Cardiovascular (CV) and Death sections of the CRF will be required to be completed. These sections include questions regarding cardiovascular (including sudden cardiac death) and non-cardiovascular death.

The CV CRFs are presented as queries in response to reporting of certain CV Medical Dictionary for Regulatory Activities (MedDRA) terms. The CV information should be recorded in the specific cardiovascular section of the CRF within one week of receipt of a CV Event data query prompting its completion.

The Death CRF is provided immediately after the occurrence or outcome of death is reported. Initial and follow-up reports regarding death must be completed within one week of when the death is reported.

9.2.6. Pregnancy

Details of all pregnancies in female participants will be collected after the start of study treatment and until the end of the pregnancy (delivery or termination).

- If a pregnancy is reported, the investigator should inform VH/GSK within 24 hours of learning of the pregnancy and should follow the procedures outlined in [Appendix 5](#).
- Abnormal pregnancy outcomes (eg, spontaneous abortion, fetal death, stillbirth, congenital anomalies, ectopic pregnancy) are considered SAE.

9.3. Treatment of Overdose

For this study, any dose of the assigned study treatment greater than the assigned dose within a 30-hour time period will be considered an overdose.

VH/GSK does not recommend specific treatment for an overdose. The investigator will use clinical judgment to treat any overdose.

In the event of an overdose, the investigator should:

1. Contact the Medical Monitor immediately.
2. Closely monitor the participant for AE/SAE and laboratory abnormalities until study treatment can no longer be detected systemically (at least 5 days).
3. Obtain a plasma sample for PK analysis within 7 days from the date of the last dose of study treatment if requested by the Medical Monitor (determined on a case-by-case basis).
4. Document the quantity of the excess dose as well as the duration of the overdosing in the CRF.

Decisions regarding dose interruptions or modifications will be made by the investigator in consultation with the Medical Monitor based on the clinical evaluation of the participant.

9.4. Safety Assessments

Planned time points for all safety assessments are provided in the SOA (Section 2).

9.4.1. Physical Examinations

- A physical exam will include, at a minimum, assessments of the skin, heart, lungs, and abdomen (liver and spleen)
- Investigators should pay special attention to clinical signs related to previous serious illnesses.

9.4.2. Vital Signs

- Pulse rate, respiratory rate, and blood pressure will be assessed.

- Blood pressure and pulse measurements will be assessed with a completely automated device. Manual techniques will be used only if an automated device is not available.
- Blood pressure and pulse measurements should be preceded by at least 5 minutes of rest for the participant in a quiet setting without distractions (eg, television, cell phones).
- Vital signs will be measured in a semi-supine position after 5 minutes rest and will include, systolic and diastolic blood pressure, and pulse and respiratory rate. Three readings of blood pressure and pulse will be taken. The first reading should be rejected. The second and third readings should be averaged to give the measurement to be recorded in the CRF.

9.4.3. Electrocardiograms

- Triplicate and Single 12-lead ECG will be obtained as outlined in the SOA (see Section 2) using an ECG machine that automatically calculates the heart rate and measures PR, QRS, QT, and QTcF intervals. Refer to Section 8.1.2 for QTcF withdrawal criteria and additional QTcF readings that may be necessary.
- At each time point at which triplicate ECG are required, 3 individual ECG tracings should be obtained as closely as possible in succession, but no more than 2 minutes apart. The full set of triplicates should be completed in less than 4 minutes.

9.4.4. Clinical Safety Laboratory Assessments

- Refer to [Appendix 2](#) for the list of clinical laboratory tests to be performed and to the SOA for the timing and frequency.
- The investigator must review the laboratory report, document this review, and record any clinically relevant changes occurring during the study in the AE section of the CRF. The laboratory reports must be filed with the source documents. Clinically significant abnormal laboratory findings are those which are not associated with the underlying disease, unless judged by the investigator to be more severe than expected for the participant's condition.
- All laboratory tests with values considered clinically significantly abnormal during participation in the study or within 2 days after the last dose of study treatment should be repeated until the values return to normal or baseline or are no longer considered significantly abnormal by the investigator or medical monitor.
- If such values do not return to normal/baseline within a period of time judged reasonable by the investigator, the etiology should be identified and the sponsor notified.
- All protocol-required laboratory assessments, as defined in [Appendix 2](#), must be conducted in accordance with the laboratory manual and the SOA.
- Refer to the SRM for appropriate processing and handling of samples to avoid duplicate and/or additional blood draws.

- All study-required laboratory assessments will be performed by a central laboratory.

NOTE: Local laboratory results are only required in the event that the central laboratory results are not available in time for either a treatment and/or response evaluation to be performed. If a local sample is required, it is important that the sample for central analysis is obtained at the same time. Additionally, if the local laboratory results are used to make either a treatment or response evaluation, the results must be entered in the CRF.

9.4.5. Suicidal Risk Monitoring and Management of Emergent Psychiatric Symptoms

GSK3640254 is not a CNS active drug nor is it being developed for a neurologic or psychiatric condition. However, given the risk of suicidal ideation identified with previous MI GSK3532795, all participants will undergo screening using the C-SSRS administered by a clinician (or qualified designee); any positive (abnormal) response confirmed by the investigator, will exclude them from participating. A repeat assessment will be done at the end of the treatment phase of the study. In case of positive (abnormal) response confirmed by the investigator, the patient will discontinue from the trial and the PI/SI will arrange for urgent specialist psychiatric evaluation and management.

As described in Section 8.1.3, new onset suicidal ideation at any time will result in immediate discontinuation from the trial and the PI/SI will arrange for urgent specialist psychiatric evaluation and management.

The definitions of behavioural suicidal events used in this scale are based on those used in the Columbia Suicide History Form [Posner, 2007]. Questions are asked on suicidal behaviour, suicidal ideation, and intensity of ideation. Screening visit questions will be in relation to lifetime experiences and current experiences (within the past 2 months) and all subsequent questioning in relation to the last assessment.

Emergent non-suicidal Psychiatric AE Evaluation and Management:

- Any Grade 1 or 2 Psychiatric AE: A Grade 1 or 2 Psychiatric AE may result in additional unscheduled visits (in-clinic or at home) as clinically indicated. This may include a more in-depth assessment of AE through interview, additional unscheduled clinical labs, and/or imaging. Psychiatric consultation may be required at the discretion of the PI/SI. Any pharmacotherapy should be discussed with the medical monitor.
- Any Grade 3 or 4 Psychiatric AE: As described in Section 8.1.3, a Grade 3 or 4 Psychiatric AE will result in discontinuation from the trial and emergency psychiatric evaluation (including potential hospitalization and pharmacotherapy as indicated).

9.4.6. GI Toxicity Evaluation and Monitoring Plan

Pre-clinical toxicology studies in rats and dogs have suggested a potential for GI related toxicity with GSK3640254. This section provides general guidance to the Investigator on

the evaluation and management of primarily upper gastrointestinal symptoms (Table 3). The Investigator may contact the VH Medical Monitor to discuss evaluation and management (including discontinuation of a participant) of any GI symptoms throughout the trial.

Table 3 GI Toxicity Evaluation and Management

HISTORY	For symptoms of all grades, a thorough history forms the foundation of proper evaluation and management. The following are potential manifestations of some GI clinical syndromes that may occur (possibly in combination) during the clinical trial.
Nausea and Vomiting	The investigator should attempt to identify the etiology of these symptoms (and whether it is intraperitoneal, extraperitoneal, medication related, infection related, or due to a metabolic disorder (Hasler, 2012). Medications can cause nausea and vomiting acutely.
Dyspepsia	The Investigator should identify the presence of red flags (odynophagia, unexplained weight loss, recurrent vomiting, GI bleeding, jaundice, palpable mass or adenopathy, or family history of GI malignancy). Symptoms of dyspepsia could include early satiety, bloating, or belching. Additionally, atypical symptoms of dyspepsia could include: pharyngitis, asthma, bronchitis, hoarseness, chest pain, or abdominal pain.
Other Clinical Syndromes	Additional diagnostic criteria for other GI disorders potentially encountered in the clinical trial are available elsewhere (Rome Foundation, 2014).
PHYSICAL EXAMINATION	Physical examination should complement elements obtained from the history (Hasler, 2012). Acutely, the investigator may assess for signs of intravascular volume depletion (eg, orthostasis) and/or aspiration of vomitus as appropriate. Abdominal tenderness and guarding may indicate inflammation. The presence of fecal blood can indicate mucosal damage (eg, from an ulcer). Complete evaluation of dyspepsia should include an oral examination (poor dentition or pharyngeal erythema) and lungs for wheezing.

DIAGNOSTIC EVALUATION AND MANAGEMENT	A major goal in the diagnostic evaluation of a participant with upper GI symptoms is to quickly arrive at a final diagnosis without exposing the participant to unnecessary (invasive) testing; Investigators should exercise good clinical judgment in this regard (Soll, 2009). A major goal of therapy is directed at correcting the underlying identifiable medical or surgical abnormalities. Consultation (eg, gastroenterologist) is recommended as clinically indicated.
Grade 1 symptoms	Participants may be treated symptomatically. If participants develop dyspepsia alone, generally only limited and direct diagnostic testing should be performed. If the participant has dyspepsia they should limit alcohol, caffeine, chocolate, tobacco, and eating directly before bedtime.
Grade 2 symptoms ^a	
Diagnostic testing may include but is not limited to the following (as clinically indicated):
 
Serum chemistries and assessment of hemoglobin if not recently performed.
 
Testing for Helicobacter pylori
 
Polymerase chain reaction (PCR) for viruses (eg, Cytomegalovirus [CMV])
 
For participants who are infected with H. pylori discontinuation from the trial is necessary. Management should be targeted at addressing the underlying pathology.

Grade 3 symptoms ^a	
Diagnostic testing may include but is not limited to the following (as clinically indicated):
 
 • The testing outlined above in Grade 2 • A barium swallow • CT scan to identify gastrointestinal inflammation • Upper endoscopy with biopsy as indicated (eg, mucosal injury or the presence of red flags). 
Management should be targeted at addressing the underlying pathology.

Grade 4 symptoms ^a	
Diagnostic testing may include but is not limited to the following (as clinically indicated):
 
 • The testing outlined above in Grade 2 and Grade 3 • An acute abdominal series 
Initial management can include correction of hemodynamic and electrolyte abnormalities as clinically indicated. After stabilization, management should be targeted at addressing the underlying pathology.

-------------------------------	---

a. A Grade 4 or related Grade 3 AE: the Investigator will discontinue the participant from the study and perform an evaluation/management plan incorporating elements above.

9.5. Pharmacokinetics

- Whole blood samples of approximately 5 mL will be collected for measurement of plasma concentrations of GSK3640254 as specified in the SOA. A maximum of 5 samples may be collected at additional time points during the study if warranted and agreed upon between the investigator and the sponsor. Instructions for the collection and handling of biological samples will be provided by the sponsor. The actual date and time (24-hour clock time) of each sample (as well as each subsequent dose) will be recorded.
- Samples will be used to evaluate the PK of GSK3640254. Each plasma sample will be divided into aliquots as outlined in the laboratory manual. Samples collected for analyses of GSK3640254 plasma concentration may also be used to evaluate safety or efficacy aspects related to concerns arising during or after the study.
- Once the plasma has been analysed for GSK3640254, any remaining plasma may be analysed for other compound-related metabolites and the results reported under a separate protocol.

Drug concentration information that may unblind the study will not be reported to investigative sites or blinded personnel until the study has been unblinded.

Intensive PK sampling (Clinic Visit 1 and Clinic Visit 5) begins with a morning pre-dose sampling, i.e, prior to the administration of the morning dose of the study treatment on the day of the visit. The pre-dose sampling should be done approximately 24 hours after the morning doses of the study drugs were taken the day prior to the visit. This pre-dose blood sampling will include the collection of the other parameters as well.

The subsequent 8 time points include samplings through Hour 12, with a final sample collected at Hour 24. The subject will either stay overnight or will return to the clinic so that the final sample can be collected at Hour 24.

It is critical to capture the exact date and time of each PK sample collection, even if drawn slightly off-schedule. If a sample collection time point is missed/late/not done within the specified window and the next collection time point has not yet been reached, collect the missed time point, and record the exact time of that collection, then get back on track for the next time point/on-time collection.

[Table 4](#) below lists the sampling schedule to be followed for the assessment of intensive pharmacokinetics. Further details of PK blood collection and sample processing will be provided in the central clinical laboratory manual.

Table 4 Intensive Pharmacokinetic Sampling Schedule and Other Activities at Clinic Visit 1 and Clinic Visit 5

	Time (Event)	Window for blood draw	Time (Relative to Dosing) Hour: Min
Clinic Visit 1 And Clinic Visit 5	morning pre-dose work: ECGs, vitals and full blood draw to include the pre-dose PK collection		
	Eat Meal. Administer study treatment and start the clock for subsequent blood draws.		00:00
	1 hr PK blood draw	± 5 minutes	01:00
	2 hr ECG and PK blood draw	± 15 minutes	02:00
	3 hr PK blood draw	± 15 minutes	03:00
	4 hr ECG and PK blood draw	± 15 minutes	04:00
	5 hr PK blood draw	± 15 minutes	05:00
	6 hr ECG and PK blood draw	± 15 minutes	06:00
	8 hr PK blood draw	± 30 minutes	08:00
	12 hr PK blood draw	± 2 hours	12:00
Next Day	24 hr (morning pre-dose) PK blood draw ^{1,2}	± 2 hours	24:00
	Eat Meal and administer study treatment.		

1. This 24-hr pre-dose PK blood draw will be done at the same time as the collection for the lab kit on the next day.

2. In study Part 1, if the Visit 5 Intensive PK visit is done on Day 10, this 24-hr PK blood draw will be done at the same time as the collection for the lab kit on Day 11. Otherwise, this 24-hr blood draw is the only draw done on Day 9 (if the clinic visit is done on Day 8) or Day 10 (if the clinic visit is done on Day 9).

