A qualified participant will be randomized into the treatment phase of the study and will administer study treatments, once daily, from Day 1 through Day 10 in Part 1 and from Day 1 through Day 7 in Part 2. On Day 1, an appropriate number of bottles will be dispensed, with a supply sufficient to cover the entire treatment period. The blinded bottles will contain capsules of either the active dose or placebo. Dosing instructions will be indicated on each bottle. Participants will bring the bottles of study treatments to each visit, so that study treatment can be administered in the clinic after the study procedures have been performed.

Each dose of study medication will be taken with approximately 240 mL (8 ounces) of water following ingestion of a moderate calorie and fat meal (i.e. at least 400 calories, with at least 120 calories from fat), that is required to be completed within 30 minutes prior to dosing. A moderate calorie and fat breakfast is planned to be similar to the following (additional meal suggestions will be included in the Study Reference Manual [SRM]):

- 2 slices of bread
- 10 g of butter
- 20 g of jam
- 15 g of cheese
- 175 mL of apple juice

Study treatments should be administered near the same time each morning, within a 2-hr window.

On days when the participant self-administers the study treatments, observed dosing with a site staff member may be achieved as locally permitted using various forms of video calling (when at all possible) such as FaceTime, Skype, WhatsApp.

Participants will then enter the post-dosing period:

Study Part 1:

There are 4 in-clinic visits in the Part 1 post-dosing period: 3 visits for PK and other assessments during the 7 days immediately following the last dose, and a final follow-up visit primarily for safety (e.g., to follow any AEs to resolution) approximately 8-14 days after the last dose, as shown in the Part 1 Schedule of Activities (SOA, Section 2). In Part 1, participants should not start other medicines and will not start ARVs during the post-dosing period until they have completed the final follow-up visit.

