In the shortest course for Part 1, a participant can be screened/qualified, treated and assessed for all the planned visits (including the final follow-up visit) in approximately 30 days (if, for example, only 10-14 days are needed for the screening period and the final follow-up visit is performed on Day 18). In the longest course for Part 1, a participant can be screened/qualified, treated and assessed for all the planned visits (including the final follow-up visit) in 52 days (if, for example, 28 days are needed for the screening period and the final follow-up visit is performed on Day 24).

Study Part 2:

There are 2 in-clinic visits in the Part 2 post-dosing period: 1 visit for PK and other assessments on the day immediately following the last dose, and a final follow-up visit primarily for safety (e.g., to follow any AEs to resolution) 3-5 days after the last dose, as shown in the Part 2 Schedule of Activities (SOA, Section 2).

In Part 2, participants will start Investigator-selected, prescribed and provided cART immediately following the completion of the primary endpoint, i.e., the measurement of HIV-1 RNA on Day 8.

In the shortest course for Part 2, a participant can be screened/qualified, treated and assessed for all the planned visits (including the final follow up visit) in approximately 24 days (if, for example, only 10-14 days are needed for the screening period and the final follow-up visit is performed on Day 10). In the longest course, a participant can be screened/qualified, treated and assessed for all the planned visits (including the final follow-up visit) in 40 days (if, for example, 28 days are needed for the screening period and the final follow-up visit is performed on Day 12).

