	Clinic Visit 1	Clinic Visit 2	Clinic Visit 3	Virtual	Clinic Visit 4	Virtual	Virtual	Clinic Visit 5	Virtual	Virtual	Clinic Visit 6	Clinic Visit 7	Clinic Visit 8	Clinic Visit 9
Single, Pharmacokinetic (PK) sample (pre- dose at Visits 3 and 4)			X		X						X ⁷	X	X	
Intensive PK sampling ⁸ (with sample at 24hr time point the next morning)	X							X ⁹						
Observed dosing with GSK3640254/plac ebo ³	X	X	X	X	X	X	X	X	X	X				
IWRS (RAMOS) activity ¹⁰	X													

1. Procedures should be performed in the following order: ECG, Vitals, Blood Draws, followed by dose administration.
 2. The study requires 9 in-clinic visits. Flexibility is offered for Visits 3, 4, 5, 8 and 9. The visit schedule for each participant should be pre-planned to be sure weekend, work schedules and clinic hours are appropriately considered. No visit interval during the treatment period can be greater than 3 days.
 3. These assessments must be conducted with a participant during each day indicated, to include the days when the participant is not in the clinic. This can be done in via phone, preferably via a visual method (as locally permitted) of Skype, Facetime, WhatsApp, et. al.
 4. Physical Exam will include, at a minimum, assessments of the Skin, Heart, Lungs, and Abdomen (liver and spleen).
 5. Genotypic/Phenotypic testing will be conducted on Day 1 and Day 11 samples, with other visits tested as appropriate.
 6. Plasma samples for storage will be collected at each visit starting at Day 1, including unscheduled visits. These samples will be used when needed, such as when samples are lost or where quantity is insufficient for testing. In the event samples are not used by study completion, they will be utilized for additional research on ARV resistance and/or HIV-1 disease biology/host immune response (excluding any human genetic testing)
 7. If the Intensive PK day occurs on Day 10, do not collect the Day 11 pre-dose PK sample (as it is redundant with the 24-hr PK collection (completing the sample set started on Day 10).
 8. Intensive Plasma PK samples will be collected as outlined in [Table 4](#) in Section 9.5
 9. If Day 8 or 9 is the Clinic Visit 5 to include the Intensive PK collection, the participant must return the following day for the 24-hr PK collection, meal and dosing. The assessments to be done as indicated on what is a “virtual visit day” should be captured as a virtual visit, even if the questions are asked in the clinic.

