Procedure ¹	Treatment Period Day 1 – Day 7						Post-Dosing Follow Up Period	Final Follow- up	
	Day 1	Day 2	Day 3, 4 Choose one day for the Clinic Visit 3. The other day will be a virtual event.		Day 5, 6 Choose one day for the Clinic Visit 4. The other day will be a virtual event.		Day 7	Day 8	Day 10, 11 or 12
	Clinic Visit 1	Clinic Visit 2	Clinic Visit 3	Virtual	Clinic Visit 4	Virtual	Clinic Visit 5	Clinic Visit 6	Clinic Visit 7
Clinical Procedures									
12-lead ECG (triplicate reading, done pre-dose; single readings at PK draws 2hr, 4hr, and 6hr)	X								
12-lead ECG (single reading, done pre-dose at Visits 2 and 3)		X	X						X
12-lead ECG (single reading done pre-dose and at PK draws 2hr, 4hr, and 6hr)							X		

Procedure ¹	Treatment Period Day 1 – Day 7						Post-Dosing Follow Up Period	Final Follow- up	
	Day 1	Day 2	Day 3, 4 Choose one day for the Clinic Visit 3. The other day will be a virtual event.		Day 5, 6 Choose one day for the Clinic Visit 4. The other day will be a virtual event.		Day 7	Day 8	Day 10, 11 or 12
	Clinic Visit 1	Clinic Visit 2	Clinic Visit 3	Virtual	Clinic Visit 4	Virtual	Clinic Visit 5	Clinic Visit 6	Clinic Visit 7
Pharmacogenetics (PGX) Collection (if consented)	X								
Hematology/Chem istry/Urine	X	X	X		X		X	X	X
Fasting Lipid Panel (approximately 8 hrs)	X							X	X
Lymphocyte T-cell subsets (CD4, CD8)	X							X	
Plasma for HIV-1 genotype/phenoty pe ⁵	X	X	X		X		X	X	
Plasma for storage ⁶	X	X	X		X		X	X	X

Procedure ¹	Treatment Period Day 1 – Day 7						Post-Dosing Follow Up Period	Final Follow- up	
	Day 1	Day 2	Day 3, 4 Choose one day for the Clinic Visit 3. The other day will be a virtual event.		Day 5, 6 Choose one day for the Clinic Visit 4. The other day will be a virtual event.		Day 7	Day 8	Day 10, 11 or 12
	Clinic Visit 1	Clinic Visit 2	Clinic Visit 3	Virtual	Clinic Visit 4	Virtual	Clinic Visit 5	Clinic Visit 6	Clinic Visit 7
HIV-1 RNA	X	X	X		X		X	X	X
Single, Pharmacokinetic (PK) sample done pre-dose			X		X				
Intensive PK sampling (to include the 24hr samples drawn the next day)	X						X		
Observed dosing with GSK3640254 /placebo ³	X	X	X	X	X	X	X		

Procedure ¹	Treatment Period Day 1 – Day 7						Post-Dosing Follow Up Period	Final Follow- up	
	Day 1	Day 2	Day 3, 4 Choose one day for the Clinic Visit 3. The other day will be a virtual event.		Day 5, 6 Choose one day for the Clinic Visit 4. The other day will be a virtual event.		Day 7	Day 8	Day 10, 11 or 12

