	Clinic Visit 1	Clinic Visit 2	Clinic Visit 3	Virtual	Clinic Visit 4	Virtual	Clinic Visit 5	Clinic Visit 6	Clinic Visit 7
Observed dosing with Investigator-selected, prescribed and provided CART, and eCRF completion								X	
IWRS (RAMOS) activity ⁸	X								

1. Procedures should be performed in the following order: ECG, Vitals, Blood Draws, followed by dose administration.
 2. The study requires 7 in-clinic visits. Flexibility is offered for Visits 3, 4 and 7. The visit schedule for each participant should be pre-planned to be sure weekend, work schedules and clinic hours are appropriately considered. No visit interval during the treatment period can be greater than 3 days.
 3. These assessments must be conducted with a participant during each day indicated, to include the days when the participant is not in the clinic. This can be done in via phone, preferably via a visual method (as locally permitted) of Skype, Facetime, WhatsApp, et. al.
 4. Physical Exam will include, at a minimum, assessments of the Skin, Heart, Lungs, and Abdomen (liver and spleen).
 5. Genotypic/Phenotypic testing will be conducted on Day 1 and Day 8 samples, with other visits tested as appropriate.
 6. Plasma samples for storage will be collected at each visit starting at Day 1, including unscheduled visits. These samples will be used when needed, such as when samples are lost or where quantity is insufficient for testing. In the event samples are not used by study completion, they will be utilized for additional research on ARV resistance and/or HIV-1 disease biology/host immune response (excluding any human genetic testing)
 7. Intensive Plasma PK samples will be collected as outlined in [Table 4](#) in Section 9.5
 8. Log in to RAMOS on Day 1 to dispense blinded study treatment. Subsequently log-in to RAMOS for study treatment supply as needed. If a participant is discontinued from the study early, log in to RAMOS to record the discontinuation.
- The timing and number of planned study assessments, including safety, efficacy, pharmacokinetic, pharmacodynamic/biomarker assessments may be altered during the course of the study based on newly available data (e.g., to obtain data closer to the time of peak plasma concentrations) to ensure appropriate monitoring.

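### Protocol Table 4's unrestricted next-day meal-and-dose line, read literally, calls for an eighth study-drug dose on Day 8 of Part 2

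*Protocol*

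**What the plan says.** Table 4 in Protocol Section 9.5 sets out sampling and other activities for the two intensive PK days, Clinic Visit 1 and Clinic Visit 5. It serves both parts: the Part 2 Schedule of Activities (SoA, Section 2.2), footnote 7, reads "Intensive Plasma PK samples will be collected as outlined in" and points to it. Its next-day block has a 24-hour blood draw, labelled as a morning pre-dose sample, followed by "Eat Meal and administer study treatment". Neither table footnote concerns the dose. Footnote 1 is about timing the draw with the lab kit. Footnote 2 is confined to Part 1 and ties the draw to the Day 11 kit: "if the Visit 5 Intensive PK visit is done on Day 10, this 24-hr PK blood draw will be done at the same time".

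The dosing calendar is fixed elsewhere:

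- **Synopsis, Treatment Groups and Duration:** treatment is taken "once daily, from Day 1 through Day 10 in Part 1 and from Day 1 through Day 7 in Part 2".
- **Synopsis, Part 2 post-dosing period:** Day 8 is "1 visit for PK and other assessments on the day immediately following the last dose".
- **Part 2 SoA:** the row "Observed dosing with GSK3640254 /placebo" is blank on Day 8. A separate row for observed cART dosing is marked that day.
- **Section 7.8:** cART is given in clinic on Day 8, after the blood collection.
- **SAP Section 6.2.6:** 10 doses are expected in Part 1 and 7 in Part 2.

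For Part 1, SoA footnote 9 does limit next-day dosing: "If Day 8 or 9 is the Clinic Visit 5 to include the Intensive PK collection", then "the participant must return the following day for the 24-hr PK collection, meal and dosing". Table 4 does not repeat that limit, and the Part 2 SoA has no equivalent note.

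**The concern.** The line suits Visit 1, where the next day is Day 2, and a Part 1 Visit 5 on Day 8 or 9, where the next day is still a dosing day. It does not suit Part 2. There Visit 5 is always Day 7, the last dosing day, so the next day is always Day 8, after dosing has ended.

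At stake is one unintended dose of study drug on the day cART starts. The amendment cut Part 2 to seven days and moved cART forward to lower the risk of emergent resistance (Section 3.2.4). A remaining instruction to give study drug on Day 8 runs against that change. It is also an instruction that staff act on, in the table they have open on the intensive PK days, and not background text.

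**Working it through.** **Inputs.** Visit 5 is Day 8, 9 or 10 in Part 1 and Day 7 in Part 2 (SoA; SAP Section 9.1.1.2). Planned dosing is Days 1–10 and Days 1–7 (Synopsis). Expected doses are 10 and 7 (SAP Section 6.2.6). Part 2 dose levels are 40, 80 and 140 mg (SAP Section 2.3).

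**Step 1: reproduce the plan's own count.** The study-drug row of the SoA has 10 marks in Part 1 and 7 in Part 2. These match the SAP's 10 and 7.

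**Step 2: add Table 4's next-day dose, read literally.**

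| Intensive PK visit | Next day | Planned dosing day? | Total doses |
|---|---|---|---|
| Visit 1, either part (Day 1) | Day 2 | Yes | unchanged |
| Visit 5, Part 1, Day 8 | Day 9 | Yes | 10 |
| Visit 5, Part 1, Day 9 | Day 10 | Yes | 10 |
| Visit 5, Part 1, Day 10 | Day 11 | No | 10 + 1 = 11 |
| Visit 5, Part 2, Day 7 | Day 8 | No | 7 + 1 = 8 |

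**Step 3: compliance under the SAP formula** (100 × actual cumulative dose / expected cumulative dose), Part 2:

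- 40 mg: 320/280
- 80 mg: 640/560
- 140 mg: 1120/980

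Each equals 8/7 = 114.3%, which falls in the SAP's above-100% category.

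**Step 4: is the Part 1 Day 10 row live?** No. SoA footnote 9 restricts next-day dosing to a Visit 5 on Day 8 or 9, and the Day 11 study-drug cell is blank. Part 1 was also complete when this version of the protocol was written: Section 3.2.4 reports its results, and describes the Visit 5 genotype samples as Day 8 or 9.

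**Step 5: effect on Day 8 data.** SoA footnote 1 puts blood draws before dose administration. The Day 8 HIV-1 RNA sample and the 24-hour PK sample are therefore taken before any Day 8 dose. The dose-response and exposure-response models in SAP Sections 10 and 11 use HIV-1 RNA through Day 8, so they are unaffected.

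**Step 6: check the correction.** Limiting the line to days within the dosing period leaves it in force after Visit 1 and after a Part 1 Visit 5 on Day 8 or 9. The totals return to 10 and 7.

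**The case against.** The strongest defence has three parts.

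1. **Definition of study treatment.** Protocol Section 7 defines it broadly enough to include marketed products, so on Part 2 Day 8 the Table 4 line could be read as referring to cART. This does not rescue the line. Section 7.1 lists only GSK3640254 and its placebo as treatments administered, the same words on the intensive PK day itself mean study drug, and the 24-hour row is labelled pre-dose.

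2. **Purpose of the table.** Table 4 is a sampling schedule, and SoA footnote 7 refers sites to it for PK samples. That is fair, but the table's title also covers other activities, and dosing is one of the activities it lists.

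3. **Clarity elsewhere.** The Synopsis, the SoA, Section 7.8 and the SAP all end Part 2 dosing on Day 7. This stands. It makes it unlikely that a site would act on the line, and it is why the point is minor.

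A reader might infer more than the documents support:

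- **The Part 2 regimen is ambiguous.** It is not. One table line disagrees with several clear statements.
- **The Day 8 efficacy result is at risk.** It is not, because the sample precedes any dose.
- **Monotherapy would be extended.** The extra dose would be taken with the first cART dose, so it would not add a day of monotherapy. Two of the 20 planned Part 2 participants receive placebo and would get no extra drug.
- **PK results would change.** With the healthy-participant half-life of 22 to 29 hours (Section 3.2.2) and mono-exponential decline assumed, an extra dose would roughly double residual concentrations at Visit 7: 2^(24/29) = 1.77 to 2^(24/22) = 2.13 times. But no PK sample is scheduled at Part 2 Visit 7, so no planned PK result is touched.
- **The all-visit maximum change would be distorted.** Visit 7 enters that summary (SAP Section 10.1.4), but it follows the start of cART whether or not this line exists. Any added effect cannot be derived from the documents.
- **Participants would leave the per-protocol set.** SAP Appendix 1, item 8, lists incorrect administration of study drug. Exclusion is possible but not established.

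**Conclusion.** Table 4 is wrong as written for Part 2, and the point is minor. Read literally, it gives 8 doses against 7 planned, or 114.3% compliance, to any Part 2 participant whose site follows it. The consequence is one possible unintended dose alongside the first cART dose. The likelihood is low because the SoA and Section 7.8 are clear, and the documents give no basis for a figure. The Day 8 HIV-1 RNA value and the models through Day 8 stand.

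The same wording is loose for a Part 1 Visit 5 on Day 10, where it would give 11 doses against 10 (110.0%). SoA footnote 9 covers that case and Part 1 is complete, so it adds nothing to the point.

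The conclusion assumes that study treatment in Table 4 means GSK3640254 or placebo, as Section 7.1 indicates, and that procedures follow the stated order of blood draws before dosing.

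**What to change.** In Table 4, limit the next-day meal-and-dose line to days within the dosing period: after Visit 1, and after a Part 1 Visit 5 on Day 8 or 9, in line with SoA footnote 9. Add a footnote on Part 2: after Visit 5 (Day 7), only the 24-hour PK draw from this table is done on Day 8; no GSK3640254 or placebo is given; cART starts after the blood collection, as in the SoA and Section 7.8. The pre-dose label on the 24-hour row should be dropped for that case.

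The cost is one table line and one footnote, in a protocol clarification or the next amendment. No data collection or analysis changes.
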